6. BIOSTATISTICAL ANALYSIS

Overview

Data acquisition and analytics approaches will be performed by [name] under the supervision of biostatistician [name]. To characterize our sample, data will be displayed graphically, and summary statistics (e.g., means and frequencies) will be calculated for all variables, including demographic and clinical descriptors. Descriptive statistics and exploratory graphing (e.g., scatter plots) will be used to assess normality, skew, and outliers on all measures. Continuous measures will be transformed if necessary, to satisfy assumptions of normality and homogeneity of variance.

Baseline differences between the treatment arms (AR-ERT vs. SPT) in demographic and other potential prognostic variables will be examined using chi-square analyses for discrete variables and ANOVA for continuous variables. While randomization tends to produce well-balanced treatment samples, if we find significant differences in potentially important baseline variables, we will include these variables as covariates in subsequent multivariate analyses. Candidate covariates for adjustment include baseline values of RNT (PTQ-PW score), symptom measures (Y-BOCS, SIGH-A, SIGH-D), and use of psychotropic medication (yes/no). Additional covariates that are unlikely to moderate treatment effect, but nonetheless will be examined for completeness, include: age, gender, education, race/ethnicity (majority vs. minority as we do not anticipate recruiting enough subjects from any one minority group to perform analyses for specific groups). If effects of gender and/or minority status are found that might be clinically meaningful, even if not statistically significant, we will report these to guide future research. Frequencies of adverse events (with 95% confidence intervals) will be calculated by treatment arm and type of event. We also will compare treatment groups on baseline credibility/expectancy of treatment and post-treatment satisfaction. A two-tailed p value $<.05$ will be considered evidence of statistical significance for the primary outcome.

Missing Data

Our multi-level generalized linear modeling (GLM) approach (described below under “Primary Analyses”) uses an intent-to-treat analysis that includes all participants, regardless of missing data (increasing power and generalizability), and it provides accurate estimates of regression coefficients in small samples.^{118,119} Despite our best efforts to retain participants, we do expect dropouts (i.e., subjects who are lost to follow-up or withdraw early from the study for reasons described below under “Participant Withdrawal”). We will attempt to perform all scheduled assessments for subjects who are withdrawn from the protocol and will provide financial incentives for participation in assessments.

Missing data rates and patterns will be assessed by treatment arm. Reason(s) for missing data will be documented, and we will evaluate reasons for dropout, study withdrawal, and loss-to-follow-up by treatment group. We will attempt to ascertain if missingness is occurring at random by evaluating factors associated with dropout for potential attrition bias. We will also compare study dropouts to study completers on demographic and clinical variables. Finally, we will use sensitivity analyses to quantify the impact of missing data.¹²⁰

Data Processing

For behavioral tasks that include reaction times (e.g., the Emotional Interference Task [EIT]), we will remove reaction times <150 ms given that such responses are rare and likely represent errors.¹²¹ Eye position fixations from the Attentional Engagement-Disengagement Task (AEDT) sampled at 120Hz will be converted to visual fixation data using standard criteria (i.e., minimum duration 100ms; minimum radius 1 degree).¹²²

Eye-blink artifacts will be removed from scalp-recorded EEG data on the Cued

Emotional Control Task (CECT) and during the resting-state period (0.1-100Hz, sample rate = 256Hz) using established procedures,¹²³ and gross artifacts will be rejected by visual inspection. For the CECT, cue- and target-locked event related potentials (ERPs) will be formed by segmenting EEG data around cue and stimulus onsets (from -200 ms to 1000 ms post-stimulus) and averaging the segments. Start and end points for the components of interest are: (a) cue-locked N2: 200-350ms post-cue; (b) target-locked N2: 200-350ms post-target; (c) target-locked N450: 400-500ms post-target; (d) target-locked P300: 300-600ms post-target.⁴⁹ ERPs will be rejected if there is significant artifact (e.g., amplitude $\pm 100 \mu\text{V}$) at any electrode on a given trial. Artifact-free mean amplitudes (μV) will be extracted for ERP analyses. Additionally, nonoverlapping, artifact-free 2-second epochs from the resting-state period will be extracted for source localization analyses. Building on recent source localization studies,^{80,124} seeds from key regions within the frontoparietal (FPN) and default mode (DMN) networks will be selected to create regions of interest (ROIs) based on previous published methods^{125,126} and drawing from the Montreal Neurological Institute 305 template.¹²⁷ We will then compute EEG source-based functional connectivity using exact Low Resolution Electromagnetic Tomography (eLORETA) software.⁷⁸

Primary Analyses

Due to the nested structure of the data (i.e., 4 assessments per participant), we will use a multi-level generalized linear modeling (GLM) approach to address each of our hypotheses.

Hypothesis 1: Target Engagement. To test whether participants who receive AR-ERT show greater improvements in attentional/cognitive control relative to those who receive SPT, we will run a series of GLM analyses for each index of our attentional/cognitive control target:

- 1) **Behavioral:** (a) attentional disengagement (i.e., latency of shift in gaze from emotional to neutral face surrounded by the frame; AEDT), and (b) sustained attention (i.e., difference in reaction times to tones following a negative vs. neutral stimulus on the EIT),
- 2) **Electrophysiological:** (a) proactive cognitive control in anticipation of conflict (i.e., cue-locked N2 ERP amplitudes on “opposite” vs. “actual” trials; CECT), and (b) reactive cognitive control in response to conflict (i.e., target-locked N2, N450, and P300 ERP amplitudes after the “opposite” vs. “actual” cue; CECT),
- 3) **Self-report:** Attentional Control Scale (ACS).

We will analyze each target index individually without adjusting for multiple testing¹²⁸ in order to be inclusive in identifying targets for future studies (e.g., R61/R33 proposal). Analyses will be modeled as the GLM equivalent of 2 x 3 ANOVAs with treatment condition (AR-ERT vs. SPT), time (pre-, mid-, post-treatment), and their interaction as fixed effects; the primary contrast of interest will be treatment difference at week 8 (post-treatment).¹²⁹ Repeated measures per person will be modeled with either an auto-correlation, Toeplitz, or unstructured covariance matrix (choosing the best model based on AIC and BIC).

Hypothesis 2a: Treatment Efficacy. To examine whether repetitive negative thinking (RNT) and psychiatric functioning improve during AR-ERT, we will also use GLM. Analyses will be modeled as the GLM equivalent of 2 x 4 ANOVAs with treatment condition (AR-ERT vs. SPT), time (pre-, mid-, post-treatment, follow-up), and their interaction as fixed effects; the primary contrast of interest will be treatment difference at week 8 (post-treatment), and a secondary outcome contrast will be at week 20 (3-month follow-up). Outcomes include:

- 1) **Repetitive Negative Thinking:** (a) Perseverative Thinking Questionnaire – Past Week (PTQ-PW; primary outcome), (b) Rumination Response Scale (RRS), (c) Penn State Worry Questionnaire (PSWQ), and (d) Rumination on Obsessions and Compulsions Scale (ROCS).

- 2) **Clinical Symptoms:** (a) Yale-Brown Obsessive Compulsive Scale (Y-BOCS) and Dimensional Obsessive-Compulsive Scale (DOCS), (b) Structured Interview Guide for the Hamilton Anxiety Rating Scale (SIGH-A) and State Trait Anxiety Inventory-Trait (STAI-T), (c) Structured Interview Guide for the Hamilton Depression Rating Scale (SIGH-D) and Beck Depression Inventory (BDI-II), and (d) Clinical Global Impression Scale – Severity (CGI-S).
- 3) **Psychiatric Functioning:** (a) Work and Social Adjustment Scale (WSAS), and (b) Quality of Life Enjoyment and Satisfaction Questionnaire – Short Form (Q-LES-Q-SF).

Hypothesis 2b: Target Validation. To examine the extent to which alteration in the hypothesized target (attentional/cognitive control) is related to improvements in clinical RNT outcomes, we will compute change scores from pre- to post-treatment for both the target (i.e., AEDT, EIT, CECT, ACS) and outcome measures (i.e., PTQ-PW [primary outcome], RRS, PSWQ, ROCS, Y-BOCS, DOCS, SIGH-A, STAI-T, SIGH-D, BDI-II, CGI-S, WSAS, Q-LES-Q-SF). Pearson's correlations between changes in target and changes in outcome measures will then be computed (i.e., a completers-only analysis).

Exploratory Source Localization Analyses

We will also conduct exploratory source localization analyses with a focus on the frontoparietal (FPN) and default mode (DMN) networks. Based on previous research demonstrating changes in the anterior cingulate cortex (ACC) over the course of psychosocial treatment^{130,131} and indicating that increased activity in this region predicts better treatment outcomes,^{79,132–134} we will test the following:

1. Whether changes in ACC activation are demonstrated pre/post treatment using GLM (i.e., predicting a main effect of time) and whether treatment group (AR-ERT vs. SPT) moderates this effect (i.e., treatment group x time interaction).
2. Whether baseline (week 0) rostral ACC (rACC) theta (4.5-7 Hz) current density predicts greater reduction in RNT and symptom severity as measured by the PTQ-PW and disorder-specific measures using GLM (i.e., predicting a rACC theta x time interaction) and whether treatment group (AR-ERT vs. SPT) moderates this effect (i.e., treatment group x rACC theta x time interaction).

Finally, source localization analyses will be used to investigate the neural generators of scalp-recorded EEG signals during the CECT, with a focus on the dorsal anterior cingulate cortex (dACC) and dorsolateral prefrontal cortex (DLPFC) given their roles in conflict monitoring (dACC) and conflict resolution (DLPFC), respectively.^{57,58,135–139}

Power Analysis and Sample Size

In prior studies,^{31,140} ERT significantly improved mean levels of attentional control (ACS, our self-report target; 15.6%) and reduced RNT (PTQ-PW, our primary outcome; 37.2%) from pre- to post-treatment; with effect sizes of Hedge's $g = 1.65$ and 2.36 respectively in an open trial. ERT also significantly reduced worry (PSWQ; 34.8%) and rumination (RRS; 17.6%); with effect sizes of Hedge's $g = 1.50$ and 0.74 respectively compared to a waitlist control group with contact. Our electrophysiological and behavioral targets of attentional/cognitive control have also demonstrated sensitivity to intervention in previous studies.^{40,77,141} Sixty-two patients with elevated RNT (to balance power with recruitment feasibility) will enter the study to have a sample of 52 with attrition, which is reasonable given previous 85% retention rates of ERT at post-treatment (our primary endpoint).³¹ Based on power calculations (i.e., one-way ANOVA at post-treatment, assuming a 1:1 randomization to AR-ERT vs. SPT), with $n = 52$ completers, we will have 80% power to see a difference at .05 sig. level if the true effect size is 0.8 or greater

which is within range of the previous studies cited above. Finally, with 52 people at the end of treatment, we can detect correlations between target and outcome measures of .38 or greater.

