Perseverative Thinking Questionnaire – Past Week (PTQ-PW)⁸²: The PTQ-PW is a 15-item self-report measure of transdiagnostic repetitive negative thinking within the past week. Items on the PTQ-PW are independent of disorder-specific content and inquire about thoughts as repetitive, intrusive, unproductive, and capturing mental capacity (e.g., “The same thoughts keep going through my mind again and again”). The PTQ-PW is our primary outcome measure. It will be administered at the screening visit to determine eligibility (PTQ-PW \geq 37), the assessment visits (baseline *if more than 7 days has passed since screening*, mid-treatment, post-treatment, and 3-month follow-up), and weekly during the therapy visits.

Disorder-specific presentations of RNT will additionally be captured via the following measures, which will each be collected at the clinical assessment visits (baseline, mid-treatment, post-treatment, and 3-month follow-up):

Penn State Worry Questionnaire (PSWQ)⁸³: The PSWQ is a 16-item self-report scale that measures the tendency to engage in excessive, uncontrollable, generalized worry (e.g., “I am always worrying about something”).

Rumination Response Scale (RRS)⁸⁴: The RRS is a 22-item self-report questionnaire that measures participant general responses to sad or depressed mood (e.g., “think about how sad you feel.”).

Rumination on Obsessions and Compulsions Scale (ROCS)⁸⁵: The ROCS is a 33-item self-report measure that assesses the frequency of various responses (e.g., “I distract myself with anything that comes to mind”) to intrusive thoughts or images in the past month.

Symptom Measures

The following gold-standard interview measures will be administered by the IE at the clinical assessment visits (baseline, mid-treatment, post-treatment, and 3-month follow-up) to assess OCD, GAD, and depression symptom severity respectively:

Yale-Brown Obsessive Compulsive Scale (Y-BOCS)^{86,87}: This 12-item rater-administered semi-structured scale includes a checklist of common obsessions and compulsions and rates severity (distress and impairment) of OCD symptoms over the past week.

Structured Interview Guide for the Hamilton Anxiety Rating Scale (SIGH-A)⁸⁸: The SIGH-A is a 19-item structured, clinician-administered rating scale that provides an overall measure of generalized anxiety in the past week.

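### Covariates enter only after a significant baseline test, so sub-threshold imbalance passes into the week-8 contrast and precision available from routine baseline adjustment is lost

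*Combined protocol and SAP*

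**What the plan says.** All references are to the combined protocol and SAP.

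- **Section 6, Overview.** Baseline differences between arms "will be examined using chi-square analyses for discrete variables and ANOVA for continuous variables". The consequence is conditional: "if we find significant differences in potentially important baseline variables, we will include these variables as covariates in subsequent multivariate analyses". The named candidates are baseline PTQ-PW, Y-BOCS, SIGH-A, SIGH-D and psychotropic medication use. Age, gender, education and race/ethnicity are listed separately as less likely to matter. No significance level is given for the baseline tests; the two-tailed .05 level is stated for the primary outcome.
- **Section 6, Primary Analyses, Hypothesis 2a.** The model for each outcome is given in these words: "GLM equivalent of 2 x 4 ANOVAs with treatment condition (AR-ERT vs. SPT), time (pre-, mid-, post-treatment, follow-up), and their interaction as fixed effects". On which comparison is tested, the section says: "the primary contrast of interest will be treatment difference at week 8 (post-treatment), and a secondary outcome contrast will be at week 20". Hypothesis 1 has the same form with three time points. No equal-baseline constraint and no unconditional baseline covariate is stated for either.
- **Section 5, outcome measures.** "The PTQ-PW is our primary outcome measure". It is both a Hypothesis 2a response and the first-named candidate covariate.
- **Section 5, Randomization.** Allocation is 1:1; no stratification factor is described.
- **Section 6, Power Analysis and Sample Size.** 62 patients enter and 52 complete. Power is 80% for an effect of 0.8, from a one-way ANOVA at post-treatment.

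**The concern.** After randomisation, a significant baseline difference is a chance event. Its p-value says nothing about whether the variable predicts the outcome, and prognostic value is what determines how much adjustment helps. A gate on significance therefore leaves a strongly prognostic variable unadjusted whenever its imbalance is moderate, and in a trial of this size moderate imbalance is common.

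The model offers no other protection. With complete data and free arm-by-time means, the fitted week-8 contrast is the raw difference in week-8 means. Including week 0 as a response does not by itself remove a baseline difference from that contrast. What is at stake is conditional bias in the week-8 estimate and precision that could be had without recruiting anyone.

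A secondary issue is that PTQ-PW, Y-BOCS, SIGH-A and SIGH-D are both candidate covariates and Hypothesis 2a responses. Nothing says that an outcome's own baseline stays out of its own model, where week 0 is already on the left-hand side.

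**Working it through.** **Inputs from the plan:** 62 randomised 1:1 (31 per arm), 52 completers (26 per arm), effect 0.8, two-sided 0.05. **Assumptions:** level 0.05 for the baseline tests; baseline to week-8 correlation r = 0.3, 0.5 or 0.7 (the plan gives none); equal SDs at the two visits.

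1. **The plan's own figures.** Two-sample t-test, 26 per arm, d = 0.8: power 80.7%, which agrees with the stated 80%. Retention: 62 × 0.85 = 52.7, which agrees with 52.

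2. **Threshold of the gate.** The standard error of a baseline difference in SD units is √(2/31) = 0.254. Significance needs t(0.975, 60) × 0.254 = 0.508 SD.

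3. **How often imbalance goes unadjusted.** By the normal approximation, P(|difference| > 0.25) = 0.325 and P(|difference| > 0.508) = 0.045. The gap is 0.325 − 0.045 = 0.28.

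4. **Typical size in that band.** The mean of |difference| between 0.25 and 0.508 is 2 × 0.254 × [φ(0.984) − φ(2.000)] / 0.28 = 0.35 SD. Imbalances of 0.4 SD or more that still escape the gate occur in only about 7% of trials.

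5. **Shift in the week-8 difference (r × imbalance) and power if own baseline is always adjusted for.** Adjustment divides the residual SD by 1/√(1 − r²), so the effective d is 0.8/√(1 − r²), with 26 per arm.

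| r | shift at 0.35 SD | share of 0.8 | effective d | power |
|---|---|---|---|---|
| 0.3 | 0.10 | 13% | 0.84 | 84% |
| 0.5 | 0.17 | 22% | 0.92 | 90% |
| 0.7 | 0.24 | 31% | 1.12 | 98% |

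6. **Gate against always adjusting** (40,000-replicate simulation, 31 per arm, one baseline covariate; values in order r = 0.3, 0.5, 0.7).
   - Overall type I error with the gate: 4.8%, 4.3%, 3.6%.
   - Type I error of the unadjusted test in the roughly 19% of trials with a non-significant imbalance above 0.3 SD: 6.1%, 8.8%, 10.1%. ANCOVA stays near 5%.
   - Power at d = 0.8: 87.5%, 88.4%, 88.7% with the gate, against 89.6%, 94.5%, 99.0% always adjusted. The gate recovers little of the available gain.

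7. **Own baseline as both response and covariate** (simulation, 31 per arm, four visits, assumed AR(1) correlation 0.6, baseline imbalance 0.6 SD, no true effect). The true week-8 slope on baseline is 0.6² = 0.36.
   - Unstructured covariance: the slope goes to 1.00 and the residual covariance matrix becomes singular.
   - AR(1): slope 0.56. The unadjusted week-8 difference of 0.21 becomes 0.21 − 0.6 × 0.56 = −0.13 SD.
   - Toeplitz: slope about 0.58, giving 0.21 − 0.6 × 0.58 = −0.14 SD.
   - ANCOVA on the same data: about 0.

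8. **How often step 7 could arise.** PTQ-PW alone would be significant at baseline in about 5% of trials. At least one of the four outcome-candidates would be in 1 − 0.95⁴ = 19%, if the tests were independent.

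**The case against.** **The gate does not invalidate the test.** This stands. A reader might infer inflated type I error or an overstated power figure. Step 6 shows overall type I error at or below 5%, and step 1 reproduces the stated power, which assumes no adjustment. The loss is in precision and in conditional bias for the particular trial that is run.

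**The own-baseline problem is not written into the plan.** This also stands. A reader might infer that the primary-outcome model is mis-specified. The Overview gives one general candidate list for all later analyses, and baseline PTQ-PW is a legitimate covariate for the Hypothesis 1 indices and for other Hypothesis 2a outcomes. The error needs a significant PTQ-PW imbalance and an analyst who then enters it in PTQ-PW's own model. The text permits that but does not state it. A degenerate unstructured fit would probably be noticed, and in the AR(1) example −0.13 SD is nearer the true zero than the unadjusted 0.21.

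**The candidates are clinically chosen.** This is fair. The gate is limited to variables judged potentially important, so it would be too strong to say that it admits irrelevant ones. The remaining point is that it selects among sensible candidates by chance imbalance.

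**The plan cites a pre-post methods reference.** The citation is attached to the Hypothesis 1 contrast only, and the text states no baseline constraint or adjustment.

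**The correlation is unknown.** True. The PTQ-PW ≥ 37 entry criterion may lower it for the primary outcome, so the r = 0.3 row deserves weight. Adjustment still gains there, though modestly.

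**Conclusion.** The point holds as a nearly free improvement rather than an error in the stated design. The significance gate leaves an imbalance of 0.25 to 0.51 SD on a given continuous covariate unadjusted in about 28% of trials. The average shift in the week-8 difference is then about 0.10 to 0.24 SD, or 13% to 31% of the planning effect, across r = 0.3 to 0.7. Fixed adjustment for own baseline would take power from about 81% to between 84% and 98% over the same range.

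These sizes rest on the assumed r, equal SDs and a 0.05 level for the baseline tests. The 0.51 SD threshold applies to continuous variables only; medication, gender and race/ethnicity go to chi-square tests.

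The own-baseline issue is secondary: an omission in the wording with a real consequence if it were acted on, checked here at one assumed correlation and one imbalance.

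**What to change.** 1. Delete the significance trigger in the Overview and keep the baseline table descriptive, without tests.
2. In every Hypothesis 1 and 2a model, adjust for the endpoint's own baseline in one way only. Either keep week 0 as a response with the arm means constrained equal at that visit, or use baseline as a covariate with a covariate-by-visit interaction and remove week 0 from the responses.
3. State that an outcome's baseline is never a covariate in a model where it is also a response.
4. Further covariates are optional. If any are wanted, choose them on prognostic grounds and fix them before unblinding.

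The cost is SAP wording and a few degrees of freedom. Sample size, visits and data collection do not change.
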